Exclusion Criteria	Our study population included adults aged 19-64 insured by Oregon Medicaid continuously from January 2014 through December 2015. We excluded patients without coverage on 1/1/2014 and those with coverage gaps during the study period. We excluded patients with dual Medicaid and Medicare eligibility and whose 2014-2015 eligibility did not depend on FPL (e.g. pregnant women). Of 622,513 adults aged 19-64 with any 2014 Medicaid enrollment, 230,602 (37%) remained in our sample.
Independent Variables	Insurance group, time, and their interaction terms, mean monthly expenditures.
Dependent Variables	standardized expenditures for inpatient care, prescription drugs, and total outpatient care in addition to subdivisions of outpatient: outpatient claims were classified as either emergency department, dental, mental and behavioral health, primary care evaluation, management, and procedures, specialist evaluation, management, and procedures, and primary care/specialist imaging or tests based on a hierarchical system involving procedure code, provider type, provider specialty, place of service, and associated costs.
Covariates	The patient's age, sex, racial and ethnic background, rural setting, and comorbidity level as assessed by the enhanced Charlson comorbidity index score.
Analysis Plan	Retrospective cohort study using inverse-propensity weights to adjust for differences between groups. We summarized enrollee

	utilization outcomes as mean monthly expenditures, running a separate (two-part) hurdle model for each type.
Data Set Name	NPAT, INPATIENT_Q42015, OUTPAT, OUTPATIENT_2015Q4, RX , RX_Q42015, SAMPLE, SAMPLE_with_weights FY_2015_FR_AND_CN_Table 5, Nov 2013 Fee Schedule – Excel, January 2014 Behavioral Health Fee Schedule, January 2014 Mental Health Fee Schedule – Excel
Code Location	Box at OHSU

Medicaid Coverage Accuracy in Electronic Health Records

Full Citation	Marino, M., H. Angier, S. Valenzuela, M. Hoopes, M. Killerby, B. E. Blackburn, N. [name], J. [name], B. Hatch, J. P. O' Malley and J. E. DeVoe (2018). Medicaid Coverage Accuracy in Electronic Health Records . Prev Med Reports 11 : 297–304.
Objective	To evaluate the validity of EHR data for monitoring longitudinal Medicaid coverage and assess variation by patient demographics, visit types, and clinic characteristics.

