Study Population	Oregon Medicaid patients aged 18-64 years with a Medicaid ID or Medicaid insurance recorded in the OCHIN EHR ≥1 billed health care visit (excluding dental) from 184 Oregon CHCs in the OCHIN network linked to state Medicaid records during the study time period (1/1/2013–12/31/2014). N=135,514.
Exclusion Criteria	Patients with no Medicaid record on EHR who also did not have a Medicaid ID.
Independent Variables	Insurance cohort: (1) continuously Medicaid (Medicaid recorded at all visits); (2) continuously not Medicaid (Medicaid not recorded at any visit (patients could have Medicare, private, VA/Military, worker’s compensation, or no coverage); (3) Gained Medicaid: Medicaid not recorded for all visits in 2013 and Medicaid recorded at all visits in 2014; and (4) Discontinuously Medicaid: Any combination of visit coverage that did not follow the definitions above.
Dependent Variables	The primary outcome was agreement between EHR and Medicaid data in assigning patients to one of the four cohorts.
Covariates	Patient demographics (sex, age, race, ethnicity, language, household income represented as % FPL, urban/rural, number of common chronic conditions, and number of encounters), visit and provider types, and clinic-specific (department type and customers of OCHIN's billing service) characteristics. We included the following common chronic conditions assessed

	from diagnostic codes in the EHR: hypertension, diabetes, coronary artery disease, lipid disorder, and asthma/chronic obstructive pulmonary disorder.
Analysis Plan	Visit-level: agreement, prevalence-adjusted bias-adjusted kappa (PABAK), sensitivity, specificity, positive predictive value (PPV), and negative predictive value (NPV). Patient-level: 4x4 cross-tabulation, of insurance cohorts; two-stage logistic regression.
Data Set Name	PPDA Projects → InsuranceValidation → Data → CLEAN → patients.csv, patient_pre.csv, patient_post.csv, patient_ch.csv, encs_pre.csv, encs_post.csv, agree_no_final.csv Code is included under: PPDA Projects → InsuranceValidation → Final Code
Code Location	Box at OHSU

In Low-Income Latino Patients, Post-Affordable Care Act Insurance Disparities May Be Reduced Even More than Broader National Estimates: Evidence from Oregon

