Additionally, we will partner with the state cancer registries of one or more states to complete probabilistic linkage between our patient population and reported cancer cases. It is currently unknown how well personal cancer history and related data are documented in the outpatient EHR (i.e., data contained in the ADVANCE CDRN), thus our ability to identify and characterize cancer survivors may be incomplete. A linkage with one or more state cancer registries will supplement the CDRN data by comprehensively identifying cancer survivors in our cohort. This will allow us to test and validate our EHR-based algorithms, and to evaluate post-cancer care services provided by community health centers and the impact of insurance coverage for this population.

5) Study Population

a) Number of Subjects

Approximately 2.3 million total possible subjects. All analyses will contain a subset of these subjects.

b) Vulnerable Populations

Children ages 0-18 will be included for methods development and analyses related to childhood cancer and long-term care for cancer survivors. There is little literature about childhood cancers in vulnerable populations (e.g., economically marginalized, uninsured, or Medicaid insured) and associated disparities. Furthermore, adults with a history of childhood or adolescent cancer may require special follow-up care and screening

throughout their adult lives, thus we wish to have access to their EHR records from earlier ages where available.

c) Setting

This research will be conducted in collaboration with OCHIN. OCHIN requests the OHSU IRB serve as the IRB of record for this study.

d) Recruitment Methods and Consent Process

All patients with data in the ADVANCE CDRN may be included in this study. Subsets may include only OCHIN EHR data, only Oregon OCHIN EHR data, only persons with certain diseases or conditions (*e.g.*, cancer, diabetes, obesity), etc. For analysis of expenditures, Oregon OCHIN clinics from the ADVANCE CDRN will be linked to Oregon Medicaid administrative data using Medicaid identification number; subjects found in both datasets will be included. Similarly, for cancer registry linkage analyses only patients identified in both datasets will be included in analyses.

The ADVANCE data was collected under a waiver of authorization as the data warehouse poses very little risk to patients, and it was not practical to consent the number of patients included in the dataset.

6) Procedures

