NOTE: Access to DMAP's data will only be granted if the purpose supports the administration of the Oregon Health Plan. The request must detail how the data supports the administration of the Oregon Health Plan. Purpose statement must also support each specific data element requested.

- 3. Detail the administrative, technical, and physical safeguards Requestor will use to protect the data set.** Specifically, in order to ensure that client privacy is protected and meets DHS' Health Insurance Portability and Accountability Act Of 1996, (HIPAA) privacy policies, review and agree to abide by the OHA administrative policies including:

Administrative, Technical and Physical Safeguards Policy	OHA-100-005
Client Privacy Rights Policy	OHA-100-002
De-identification of Client Information and Use of Limited Data Sets Policy	OHA-100-007
Enforcement, Sanctions and Penalties for Violations of Individual Privacy Policy	OHA-100-009
General Privacy Policy	OHA-100-001
Minimum Necessary Information Policy	OHA-100-004
Uses and Disclosures of Client or Participant Information Policy	OHA-100-003
Uses and Disclosures for Research Purposes and Waivers Policy	OHA-100-006

(See <http://www.oha.state.or.us/policy/admin/privacypolicylist.htm>). Ensure that the description meets Title II, Subtitle F of the Health Insurance Portability and Accountability Act of 1996, 42USC 1320d et.seq, and, when applicable, the Substance Abuse and Mental Health confidentiality regulations outlined in Part II of the Department of Health and Human Services, Public Health Service, 42CFR Part 2; ORSs 179.505, 192.535, 192.547.

- 4. Provide a detailed description of health information safety and privacy protocols.** Under the current business associates agreement between OCHIN and DMAP, DMAP will provide OCHIN with a file containing the requested data.

All data exchanges will be done using standard security processes with password-controlled Secured File Transfer Protocol (SFTP) access. Access will be given only to study personnel. All reports will describe results in aggregate form only.

OHSU will receive the data once the following identifiers are removed: OHP and OCHIN ID numbers, names, full addresses, and phone numbers. IRB approval has been obtained from this research at OHSU. OCHIN has requested OHSU be the IRB of record for this study.

(Agreement / Request # 3524)

INFORMATION ACCESS AGREEMENT

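### The EHR coverage-validation study admits patients partly on the EHR record it tests: if the Medicaid ID is EHR-held, its sensitivity is an upper bound for Oregon clinic patients, and it does not validate uninsured status

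*Combined protocol and SAP*

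**What the plan says.** The study is summarised in the Combined protocol and SAP, Data Analyses, in the table headed Medicaid Coverage Accuracy in Electronic Health Records.

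- Its objective reads "To evaluate the validity of EHR data for monitoring longitudinal Medicaid coverage".
- The Study Population row admits "Oregon Medicaid patients aged 18-64 years with a Medicaid ID or Medicaid insurance recorded in the OCHIN EHR", from 184 Oregon health centers, "linked to state Medicaid records during the study time period (1/1/2013–12/31/2014). N=135,514".
- The Exclusion Criteria row removes "Patients with no Medicaid record on EHR who also did not have a Medicaid ID".
- The primary outcome is whether the EHR and the state data place a patient in the same one of four coverage cohorts. Visit-level agreement, PABAK, sensitivity, specificity, PPV and NPV are also planned.
- One of the four cohorts is "continuously not Medicaid (Medicaid not recorded at any visit (patients could have Medicare, private, VA/Military"; the row goes on to name worker's compensation and no coverage.

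Other places bear on how the result is used. SAP section B.4.4 opens by describing the OCHIN data as validated and gives Aim 2 a separate uninsured group. A Decision Log entry of 02/23/16, listed under the biomarker paper, plans to use state Medicaid data to validate visit-based insurance groups. For the expenditure analysis, section 5d of the IRB protocol links EHR and state data "using Medicaid identification number; subjects found in both datasets will be included". The table gives no count of excluded patients, no information on their true Medicaid status, and no sensitivity analysis for the exclusion.

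**The concern.** An accuracy study should draw its patients independently of the test result. Here the test is the EHR's Medicaid field, and a patient gets in by having that field filled or by having a Medicaid ID. A clinic patient whom the state covered, but for whom the EHR holds neither marker, is a false negative at every visit and is never seen. A patient with neither marker who truly had no Medicaid is a true negative at every visit and is also never seen. The accuracy measures then describe a selected group.

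The stake is in later use. Aim 2 compares newly insured patients with those the EHR shows as uninsured. Patients with no Medicaid record and no ID are the ones in whom unrecorded coverage would matter most for that comparison, and this study does not examine them. Covered patients misfiled as uninsured would dilute the contrast.

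**Working it through.** **1. Is there a figure to reproduce?** No. The documents give no 2×2 table, no sensitivity or specificity, and no excluded count. The only count is the 135,514 patients retained. What follows is algebra, then illustration on assumed inputs.

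**2. Direction.** Every excluded visit is EHR-negative, so it is either a false negative (FN) or a true negative (TN). Restoring excluded visits adds only to these two cells.

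- Sensitivity = TP/(TP+FN): can only fall or stay the same.
- Specificity = TN/(TN+FP): can only rise or stay the same, and rises most if the excluded visits are mainly true negatives.
- NPV and overall agreement: each becomes a weighted average of its observed value and (1 − q), where q is the share of excluded visits that truly had Medicaid. NPV falls only if q exceeds 1 − observed NPV; agreement falls only if q exceeds 1 − observed agreement.

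**3. Size for sensitivity.** Let m be the excluded share of all truly covered visits. Then full-population sensitivity = reported × (1 − m). Both inputs are assumed:

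| Reported | m = 0 | 1% | 2% | 5% | 10% |
|---|---|---|---|---|---|
| 0.90 | 0.900 | 0.891 | 0.882 | 0.855 | 0.810 |
| 0.95 | 0.950 | 0.941 | 0.931 | 0.902 | 0.855 |
| 0.99 | 0.990 | 0.980 | 0.970 | 0.941 | 0.891 |

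**4. All measures together.** Take 135,514 retained units (patients treated as visits, for scale only). Assume 60% truly Medicaid, sensitivity 0.95, specificity 0.90 and 50,000 units excluded. Truly covered = 0.60 × 135,514 = 81,308. This gives TP = 77,243, FN = 4,065, TN = 48,785, FP = 5,421. Observed agreement is 0.60 × 0.95 + 0.40 × 0.90 = 0.930, and observed NPV is 48,785/52,850 = 0.923.

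At q = 5%, 2,500 units join FN and 47,500 join TN:

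- sensitivity = 77,243/(77,243 + 6,565) = 0.922
- specificity = 96,285/(96,285 + 5,421) = 0.947
- NPV = 96,285/(96,285 + 6,565) = 0.936
- agreement = (77,243 + 96,285)/185,514 = 0.935

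| | Observed | q = 1% | q = 5% | q = 10% |
|---|---|---|---|---|
| Sensitivity | 0.950 | 0.944 | 0.922 | 0.895 |
| Specificity | 0.900 | 0.948 | 0.947 | 0.945 |
| NPV | 0.923 | 0.956 | 0.936 | 0.912 |
| Agreement | 0.930 | 0.946 | 0.935 | 0.922 |

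On these inputs agreement improves until q passes 7.0%, and NPV until q passes 7.7%.

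**5. Uninsured status.** The reference source is state Medicaid records, which show whether a person had Medicaid and not whether they had anything else. The non-Medicaid cohort mixes no coverage with Medicare, private, military and worker's compensation cover. A correct placement in that cohort therefore says nothing about being uninsured. This would be so without any exclusion; the exclusion adds to it by dropping patients with no Medicaid marker at all.

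**6. Illustration for Aim 2.** If a fraction u of the patients labelled uninsured had in fact gained Medicaid and behaved like the newly insured, the contrast shrinks to (1 − u) of its true size. With an assumed u = 10%, the 3.35-point detectable difference in SAP B.4.4 would appear as 3.35 × 0.90 = 3.0 points. The documents give no value for u.

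**The case against.** Several stronger readings are tempting, and the documents do not support them.

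- *All wholly missed cases are removed.* They are not. A patient with a Medicaid ID, state coverage and no Medicaid recorded at any visit stays in the study and counts as a false negative throughout. Only patients with neither marker are lost.
- *Sensitivity is overstated.* This is conditional. The exclusion wording ties the record to the EHR but does not say where the ID comes from. If the ID could come from the state file, the excluded patients would be people the state never covered, m would be zero, and sensitivity would be unbiased. The inclusion row and the ID-based linkage favour an EHR-held ID without settling it. Even then, the bias is strict only if some excluded patients truly had Medicaid.
- *The study is falsely reassuring overall.* Specificity is pushed down, and the primary outcome is cohort agreement. The illustration above covers visit-level agreement only, and there agreement can rise when the excluded are restored.
- *The non-Medicaid cohort consists only of ID holders.* That fits the EHR axis of the 4×4 table. On the state axis the cohort can also hold patients with an EHR Medicaid record whom the state never covered.
- *The study claims to validate uninsured status.* Its objective is Medicaid coverage, its population row already names Medicaid patients, and no section cites it for the uninsured group. The worry is about later use.

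It is also fair to say that this table summarises a published paper, and that the Decision Log (05/09/16) places detailed inclusion and exclusion documentation in the manuscript tracker and dataset files. A missing count here does not prove that the count was never reported.

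What survives is that entry depends partly on the source under test, and nothing in the documents bounds the effect.

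**Conclusion.** The concern holds in a limited form. If the Medicaid ID is EHR-held, reported visit-level sensitivity is an upper bound for all Oregon health-center patients, by the factor (1 − m). Over an assumed m of 1% to 10%, a reported 95% would correspond to between 94.1% and 85.5%; at m = 0 there is no bias. Specificity is a lower bound, noticeably so if the excluded visits are mostly true negatives. NPV and agreement have no fixed direction. The real size cannot be computed because m, the number excluded and the reported accuracy are not in the documents.

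Separately, and whatever the source of the ID, the study cannot support the uninsured label used in Aim 2. The main reason is the pooled non-Medicaid cohort set against Medicaid-only reference data; the exclusion is a contributing reason.

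**What to change.** 1. State where the Medicaid ID comes from (EHR or state file) and how many patients and visits the exclusion removed.
2. Add a bounding analysis: restore the excluded visits and recompute sensitivity, specificity, NPV and agreement over a stated range of their true Medicaid share, as in step 4 of the working but with the study's own counts.
3. Describe every accuracy measure as applying to patients with a Medicaid record or ID in the EHR.
4. Do not cite the study as validating uninsured status in Aim 2 or in the papers that use an uninsured group.
5. If the access agreement permits, have OCHIN match the excluded patients to state enrolment on the identifiers it holds. Item 4 of the Research Application implies that it holds them: "OHSU will receive the data once the following identifiers are removed: OHP and OCHIN ID numbers, names, full addresses, and phone numbers". Comparing OCHIN with state coverage is already among that application's purposes, but permission for this particular match must be confirmed. A failed match should not be counted as certain non-Medicaid, because that turns linkage error into true negatives; include a sensitivity analysis for match failure.

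Items 1 to 4 cost a little extra analysis and a narrower, less favourable sensitivity claim. Item 5 costs a linkage and possibly a further approval. Even a perfect match would not validate uninsured status, since the reference data would still cover Medicaid only.
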